## **B. Subject Accrual and Compliance**

Measurement and Reporting of Subject Accrual, Compliance with Inclusion/Exclusion Criteria— Review of rate of subject accrual and compliance with inclusion exclusion criteria will occur during each recruitment phase to ensure that a sufficient number of participants are being enrolled and that they meet the study criteria;

### Measurement and Reporting of Participant Adherence to Treatment Protocol

Adherence will be assessed by the number of participants, using health coach (PACT only), and number of online modules completed.

## **C. Justification of Sample Size**

This is a pilot randomized clinical trial of the PACT program for TMD pain to determine feasibility and acceptability of methods and preliminary outcomes to power a multisite randomized clinical trial of its efficacy. The study is not powered to detect statistically significant intervention effects. For this study we have selected a sample size of 80 participants. This will provide an adequate sample for feasibility assessments and is in line with the constraints of available study resources and timing considerations related to the funding mechanism of the study. Comparisons done as part of the feasibility analyses of patient characteristics in each stage will serve as an alert to potential sources of bias in the study and will be used to inform refinement of the protocol for a larger study. Results from the pilot study, in conjunction with previous findings of behavioral interventions will be used to estimate the parameters needed for the study trial.

## **D. Stopping Rules**

This study will be stopped prior to its completion if: (1) the intervention is associated with adverse effects that call into question the safety of the intervention; (2) difficulty in study recruitment or retention will significantly impact the ability to evaluate the study endpoints; (3) any new information becomes available during the trial that necessitates stopping the trial; or (4) other situations occur that might warrant stopping the trial.

## **E. Designation of PI/PO in the Role of Data Safety Monitor**

The PI, [name] will provide data safety monitoring oversight for the study.

## **F. Safety Review Plan**

Study progress and safety will be reviewed following each recruitment and intervention phase – every 6 months by the Study Coordinator in collaboration with the PI. Progress reports, including patient recruitment, retention/attrition, and AEs will be provided to the PI following each of the reviews. An Annual Report will be compiled and will include a list and summary of AEs. In addition, the Annual Report will address (1) whether AE rates are consistent with pre-study assumptions; (2) reason for dropouts from the study; (3) whether all participants met entry criteria; (4) whether continuation of the study is justified on the basis that additional data are needed to accomplish the stated aims of the study; and (5) conditions whereby the study might be terminated prematurely. The Annual Report will be sent to the IRB and NIDCR. The IRB will review progress of this study on an annual basis.

### **G. Study Report Outline for the Interim or Annual Reports**

The study coordinator and statistician will prepare a study safety report which begins with a brief introduction section describing the study status, issues, and procedures that produced the report (e.g., data obtained by specific date). A study description with a current timetable and study schedule will be included. Data are presented that describe the administrative status of the study, including recruitment and forms handling. The study data report will describe demographic, baseline characteristics, subject status, and safety assessment.

#### *Study Report Outline*

- I. Table of Contents
- II. Introduction
  - a. Summary of Study Status and Issues or Problems
  - b. Report Preparation Procedures
- III. Study Description
  - a. Project Organization Chart, Personnel
  - b. Brief Statement of Purpose of Trial
  - c. Projected Timetable and Schedule
  - d. List of Any Resource Centers
- IV. Study Administration
  - a. Recruitment Status
    - i. Enrollment by Month for 6 months of enrollment
    - ii. Comparison of Targeted to Actual Enrollment
  - b. Retention Status
    - i. Overall Subject Status

- ii. Individual Subject Status
- V. Study Data Reports/Tables or Figures
- a. General Information
    - i. Enrollment (see Appendix A, Table 1)
    - ii. Demographic/Baseline Data (see Appendix A, Table 2)
    - iii. Subject Status (see Appendix A, Table 3)
  - b. Safety Assessment
    - i. Treatment Duration for All Subjects (see Appendix A, Table 3)
    - ii. AE Data
      - 1. Overall Listing (see Appendix A, Table 4)
      - 2. Specific Symptom Listing (see Appendix A, Table 5)
      - 3. Out-of-Range Values (see Appendix A, Table 6)
      - 4. SAE Listing (see Appendix A, Table 7)
      - 5. Subject Deaths (see Appendix A, Table 8)

#### **IV. Informed Consent**

A structured enrollment screening process will be implemented to assure that all subjects obtain complete information about the study and appropriate questions are asked to insure their understanding about the project prior to and during the consent process.

The SRC will contact all study participants completing the initial phone screen who are eligible and still express interest in the study. The SRC staff member will first provide a complete overview of the study and detail the requirements of study participation as specified in the consent form. The SRC will then ask whether the potential participant is still interested in study participation. If yes, they will describe the benefits and risks of study participation and discuss issues of confidentiality. Following this the SRC staff member will again ask about continued interest in the study and elicit questions from the potential participant. The participant will then be asked if they still wish to proceed. If the subject wishes to proceed, the SRC will then email the participant the study consent and HIPPA form along with a link to the website with log-in information (username and password). Subjects will be asked to visit the study website and log-in to complete the consent form electronically before continuing on in the study.

#### **V. Reporting Changes in Study Status**

During the funding of this study, any action by an IRB or one of the study investigators that results in a temporary or permanent suspension of the study will be reported to the NIDCR Program Official within 1 business day of notification.

**Data Safety and Monitoring Plan**

**Appendix A**

**Table 1. Enrollment by Month of Study**

Week #	# Expected (400 )	# Screened	# Enrolled	# Withdrawn	# Actual (#Enrolled - #Withdrawn)	# Cumulative

**Table 2. Demographics**

Characteristics	N	N%
Gender		
Female		
Male		
Ethnicity		
Hispanic or Latino		
Not Hispanic or Latino		
Unknown		
Age		
Mean (SE)		
Median (min, max)		
Race		
Asian		
Nat Hawaiian/Other Pac Islander		

Black or African American		
White		
Other		
More than one race		
Unknown		

**Table 3. Subject Status**

Pt Identifier	Date Enrolled	Date Completed Study	Study Status	Reason for Withdrawal	% Adherence to Intervention (# of Modules completed)	Intervention Duration (Weeks)

Status:

A = Active

C = Completed

W = Withdrew

L = Lost to Follow Up

% Adherence to Intervention:

(# Modules completed/total #)\*100

or

**Table 4. Adverse Events**

Pt Identifier	AE Onset	AE End	AE Description	Severity	SAE? (Y/N)	Relatedness	Action Taken	Outcome	Comments

Severity of AE:

- 1 = Mild
- 2 = Moderate
- 3 = Severe

Relatedness to Intervention:

- 1 = Definitely Unrelated
- 2 = Possibly Related
- 3 = Probably Related
- 4 = Definitely Related

Action Taken:

- 0 = None
- 1 = Dose modification
- 2 = Medical intervention  
- (specify in comments)
- 3 = Hospitalization
- 4 = Intervention discontinued
- 5 = Other

Outcome:

- 1 = Resolved
- 2 = Recovered with minor sequelae
- 3 = Recovered with major sequelae
- 4 = Continuing treatment
- 5 = Condition worsening
- 6 = Patient death\*\*

\*\*Provide further details regarding all reported serious AEs and deaths in the SAE and Subject Deaths tables listed at the end of this section.

**Table 5. Frequency of Specific Symptoms**

Symptoms	Description of AE	N%
Jaw Fatigue		
Jaw pain		
Jaw joint clicking		
Jaw joint locking		
Difficulty chewing		

**Table 6. Serious Adverse Events**

Pt Identifier	Age	Treatment Date	SAE	SAE Date	Related to Intervention	Description of Actions and Outcomes (e.g., hospitalization, withdrawn from study)
Subj001						
Subj002						
Subj003

Tailored Self-Management of TMD Pain using Health Information Technology

NIDCR Protocol Number: 16-054-E

NIDCR Grant Number: U01 DE025609

Principal Investigator: [name], MS

March 20, 2017

Final Analysis Plan

We will perform the following analysis and present results in preparation of the full study. The Primary outcomes for this study are acceptability and feasibility of the methods. The study is not sufficiently powered to test for mean changes from baseline to follow-up. Thus, we will conduct the following descriptive analysis at noted in the outcome measures:

- Number of participants, baseline characteristics and outcomes at baseline will be summarized descriptively
- Summary measures will include mean values (standard deviation SD) for continuous variables and frequency distribution for categorical variables.
- Outcome measures will be analyzed for departure of normality, and standard transformations will be applied.
- Percent of participants completing the measures for outcomes, mediating and moderating factors at baseline and each follow-up periods

The acceptability of the outcomes, mediating and moderating measures at baseline and followup periods

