## **2.3 Potential Risks and Benefits**

### **2.3.1 Potential Risks**

Potential risks include:

- 1) Although the program includes simple exercises and behavioral changes, participant conditions may not improve or may have their pain aggravated. This is minimized by providing personalized experiential instruction on the exercises and behavioral changes and cautioning participants to seek additional care if their condition does not improve or worsens. Participants will be screened by TMD diagnostic criteria to ensure their condition is appropriate for the study.
- 2) There is some risk associated with the release of personal health information (PHI) from health records. The investigators will protect subjects' records so their name, address, phone number, and clinical information is kept private and will not be released without participants' specific written permission. All data will be stored in a de-identified format without reference to participant identity.

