#### **4 STUDY DESIGN**

The pilot study design is a 2-arm randomized clinical trial to test the methods that will be used in a future proposal for a full-scale multi-site clinical trial.

Eighty participants with TMD will be recruited through 2 recruitment protocols (1-Inbound recruitment or self-referral and 2-outbound recruitment or ICD-9/ICD-10 code identification) and randomized in a 1:1 ratio to the PACT program or Traditional self-care. Participants will be aged 18 or older because significant adjustments would need to be made to the program to take into consideration the differing cognitive status and developmental age, and limited to English-speakers because one of the primary outcome instruments is only validated in English.

The study should be completed in 12-18 months, with enrollment occurring for 8 months.

Participants will be evaluated for eligibility over the telephone following verbal consent for screening, and information including demographics and eligibility criteria. Eligible participants will be consented over the telephone and will sign the consent electronically. Following consent participants will complete the baseline questionnaire and be randomized to PACT (intervention) or self-care (control). Weeks 1-8 (intermediate visits) will consist of weekly website visits. Participants in the self-care arm will be provided with traditional self-care material. Participants in the PACT arm will complete initial assessments for weekly lessons, and based on the assessment will be provided personalized lessons. Participants in the PACT arm will also receive weekly coaching sessions by phone. All participants will participate in usual care from their dentist and will be asked to limit concomitant medications to NSAIDs. Participants in both arms will complete follow-up measures at 8 and 16 weeks post-intervention. Following the 8-week follow-up participants will be asked to complete a program evaluation, and at least 10 randomly-selected subjects will complete a qualitative interview.

Data analysis will evaluate feasibility and acceptability of the primary intervention and determine the utility of the outcomes measures that will be collected at baseline, 8-week and 16-week follow-ups.

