## **5.5 Subject Withdrawal**

Participants may withdraw voluntarily from the study at any time or the investigator may terminate participation for any of the following reasons:

- Participant reports that the TMD self-care practices result in:
  - sustained increased pain,
  - the jaw locks,
  - or if the participant appears to display serious emotional difficulties, dissatisfaction or confusion with care during the lessons.
- Participant refuses to participate in any of the PACT program activities after enrollment.
- Continued participation deemed to be not in the participant's best interest.
- Investigator discretion.

Participants withdrawn after randomization will not be replaced.

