**Graded Chronic Pain**

1. On how many days in the last 30 days have you had jaw or temple pain? \_\_\_\_\_ Number of Days

2. How would you rate your jaw or temple pain RIGHT NOW?

No Pain	0	1	2	3	4	5	6	7	8	9	10	Pain as bad as could be
----------------	----------	----------	----------	----------	----------	----------	----------	----------	----------	----------	-----------	--------------------------------

3. In the **last 30 days**, how would you rate your **WORST** jaw or temple pain?

No Pain	0	1	2	3	4	5	6	7	8	9	10	Pain as bad as could be
----------------	----------	----------	----------	----------	----------	----------	----------	----------	----------	----------	-----------	--------------------------------

4. In the **last 30 days**, **ON AVERAGE**, how would you rate your jaw or temple pain?  
 That is, *your usual pain* at times you were in pain.

No Pain	0	1	2	3	4	5	6	7	8	9	10	Pain as bad as could be
----------------	----------	----------	----------	----------	----------	----------	----------	----------	----------	----------	-----------	--------------------------------

5. In the **last 30 days**, how many days did your jaw or temple pain keep you from doing your **USUAL ACTIVITIES** like work, school, or housework?

\_\_\_\_\_ Number of Days

6. In the **last 30 days**, how much has jaw and temple pain interfered with your **DAILY ACTIVITIES**, rated on a scale of 0-10, where 0 is "no interference" and 10 is "unable to carry on any activities"?

No interference	0	1	2	3	4	5	6	7	8	9	10	Unable to carry on any activities
												

7. In the **last 30 days**, how much has jaw and temple pain interfered with your **RECREATIONAL, SOCIAL AND FAMILY ACTIVITIES**, rated on a scale of 0-10 where 0 is "no interference" and 10 is "unable to carry on any activities"?

No interference	0	1	2	3	4	5	6	7	8	9	10	Unable to carry on any activities
												

8. In the **last 30 days**, how much has jaw and temple pain interfered with your **ABILITY TO WORK, INCLUDING HOUSEWORK**, rated on a scale of 0-10, where 0 is "no interference" and 10 is "unable to carry on any activities"?

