#### II. Adverse Event Information

##### A. Definition

An **adverse event (AE)** is generally defined as any unfavorable and unintended diagnosis, symptom, sign (including an abnormal laboratory finding), syndrome or disease which either occurs during the study, having been absent at baseline, or if present at baseline, appears to

worsen. Adverse events are to be recorded regardless of their relationship to the study intervention.

A **serious adverse event (SAE)** is generally defined as any untoward medical occurrence that results in death, is life threatening, requires inpatient hospitalization or prolongation of existing hospitalization, results in persistent or significant disability/incapacity, or is a congenital anomaly.

If participants screen for depression and/or suicidal ideation, we will provide a list of mental health providers who they can consult with to ensure their safety.

The study intervention is a patient-centered self-management program for TMD pain. The PACT program is a web-based, tailored 8-week program supported by a health coach to help enhance understanding, compliance, and success in self-management for TMD pain. There are self-report assessments at the end of each week throughout the entire program to monitor progress, compliance, adverse events, risk factors, and protective factors. If study subjects develop an aggravation of the pain or a new symptom that the subject attributes to the study intervention this would be considered an adverse event. This will be monitored by both self-report within the PACT program weekly assessments as well as by the dental professional who is caring for the patient. In both cases, this will be reported to the PI and PO.

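### Both arms give the same 0-10 pain ratings at baseline, week 8 and week 16, but no planned analysis uses them to count, by arm, who got worse; worsening is reported only as adverse events, under rules that conflict

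*SAP*

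**What the plan says.** **The risk.** Protocol 2.3.1 opens its list of risks with the possibility that "participant conditions may not improve or may have their pain aggravated". Section 5.5 lets the investigator end participation for "sustained increased pain".

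**The data.** Section 4 states: "Participants in both arms will complete follow-up measures at 8 and 16 weeks". The surveys in Appendix G carry the same Graded Chronic Pain items at baseline and at both follow-ups. Items 2 to 4 ask for current ("How would you rate your jaw or temple pain RIGHT NOW"), worst and average pain from 0 to 10. Item 9 asks for eight jaw limitations, each 0 to 10 or not applicable.

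**The analysis.** The SAP, which repeats Protocol 11.4, introduces its list with "Thus, we will conduct the following descriptive analysis at noted in the outcome measures". The list covers outcomes at baseline, means (SD) and frequencies, normality, percent completing each measure, and acceptability of the measures. It has no change from baseline, no count of worsened participants and no safety summary. The only target on change, in the instrument-performance table of 3.2.1, is that outcomes move the way the investigators expect.

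**Safety reporting.** This sits in Sections 8 and 11.3 and Appendix J. The Appendix J definition includes "an aggravation of the pain or a new symptom that the subject attributes to the study intervention this would be considered an adverse event". Table 5 there is a symptom frequency table with rows for jaw pain and "Difficulty chewing".

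**The concern.** The study measures its main foreseeable clinical harm directly and identically in both arms, then plans no output that uses the measurement for that purpose. What gets reported depends on someone noticing worsening, recording it as an event and, under some passages, judging it related. In an unblinded trial whose arms differ in contact with study staff, that process can run differently by arm. The scores do not depend on it.

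The pilot is meant to inform a multisite trial, and Section 11.3 asks the annual report to say whether continuing is justified. How many people in each arm got worse is relevant to both, and the plan as written does not call for that number.

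**Working it through.** The plan states no harm rate, worsening cut-off or SD of change, so there is no figure to reproduce. The check compares passages, then gives a sense of scale under stated assumptions.

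**Step 1. Can the adverse-event route supply the count?**

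- *Recorded:* Section 8.1.2 records all events, related or not, and includes conditions present at baseline that appear to worsen.
- *Defined:* Section 8.1.3 first treats any increase in pain as an event whether or not it is related, then describes aggravation that the subject attributes to the intervention. Appendix J, II.A repeats the second form.
- *Reported:* Section 8.2 limits reporting to events considered related.
- *Detected:* Section 8.1.3 relies on weekly assessments within the PACT program and on the treating dental professional. For controls, Section 6.3 mentions website assessments, which are not reproduced. Section 6.4 promises adverse-event questions at weeks 8 and 16, but the surveys in Appendix G contain none. Appendix A marks adverse-event reporting for the intervention and week 8 columns, not week 16.
- *Tabulated:* Appendix J Tables 3 (status and withdrawal reason), 4 (events) and 5 (symptoms) have no arm column.

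A participant whose mean pain rises from 4 to 8 without reporting or attributing it need not appear in any planned by-arm output.

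**Step 2. Would follow-up means reveal it?** For mean change m (negative is improvement), SD of change s and normality, the share worse by at least k points is 1 − Φ((k − m)/s). Assume m = −1.

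| SD of change | Worse by 1 or more | Of 40 | Worse by 2 or more | Of 40 |
|---|---|---|---|---|
| 1.5 | 1 − Φ(1.33) = 9.1% | 3.6 | 1 − Φ(2.00) = 2.3% | 0.9 |
| 2.0 | 1 − Φ(1.00) = 15.9% | 6.3 | 1 − Φ(1.50) = 6.7% | 2.7 |
| 2.5 | 1 − Φ(0.80) = 21.2% | 8.5 | 1 − Φ(1.20) = 11.5% | 4.6 |

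With m from 0 to −2 and the same SDs, the 1-point share runs from 35% down to 2%. An arm can improve on average while a visible minority worsens.

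**Step 3. What would the count show?** Section 11.2 gives 40 per arm. Section 3.2.1 targets 80% completing both follow-ups. Applying that to each arm is an assumption: 0.80 × 40 = 32. The 90% expected in 3.2.2 would give 36. Suppose, purely for illustration, that 8 of 32 PACT and 3 of 32 control participants worsen.

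- Exact (Clopper-Pearson) 95% CIs: 8/32 = 25.0% (11.5% to 43.4%); 3/32 = 9.4% (2.0% to 25.0%).
- Difference: 25.0 − 9.4 = 15.6 points, Newcombe 95% CI −3.3 to +33.8.
- Counting the 8 missing per arm as worsened: (8 + 8)/40 = 40.0% and (3 + 8)/40 = 27.5%. If only one arm's missing participants worsened, the difference runs from 8/40 − 11/40 = −7.5 points to 16/40 − 3/40 = +32.5 points.
- If none of 32 worsened, the two-sided exact upper limit is 1 − 0.025^(1/32) = 10.9%, for completers only. Counting 8 missing as worsened gives 8/40 = 20%.

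**Step 4. Should it be tested?** No. Power to separate 20% from 10% is about 24% with 40 per arm and 20% with 32.

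**The case against.** Much of the other side stands.

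- A reader might infer that aggravated pain is the only harm foreseen. It is not. Section 2.3.1 also says "There is some risk associated with the release of personal health information (PHI) from health records", and Section 5.5 names jaw locking and serious emotional difficulties.
- A reader might infer that no planned output counts worsened pain at all. That goes too far. Because the event definition covers a baseline condition that worsens, the jaw-pain row of Table 5 is itself a planned count of worsening. What it lacks is a link to the scores and a split by arm.
- Safety is not unplanned because the SAP omits it. Section 8.4 has the investigator ask about events at each visit and review source documents. Appendix J, III reviews self-report data for study-related events. Withdrawal reasons are recorded and listed in Table 3, and the annual report covers event rates and dropouts.
- The documents do not say that the expected-direction target is judged on means. Step 2 shows only that means would be insufficient.
- A rise in score is not in itself harm. With no true average change and the same SDs, 25% to 35% of an arm would be worse by 1 point or more.
- This is an unpowered feasibility pilot, and the scores are kept, so the table could be made later. But low power argues against a test, not against a description, and cut-offs chosen after seeing the data would carry less weight.

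**Conclusion.** The point holds in this form: neither the SAP nor Protocol 11.4 uses the common pain scores to count, by arm, participants who worsened, and the adverse-event route does not fill that gap reliably. Its reporting rules conflict, its detection is described differently for the two arms, and its tables do not show arm.

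The documents do not support the stronger inference that the pilot will report no harm while its data show it. Missed worsening is a possibility whose size they do not allow anyone to state. The 9% to 21% rests on an assumed 1-point mean improvement, SDs of 1.5 to 2.5 and normality; the counts of 8 and 3 are invented for scale. Nor would zero among completers bound the risk for a whole arm, because increased pain is a reason for ending participation and Section 5.5.1 collects nothing after consent is withdrawn.

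This is a worthwhile, inexpensive improvement to a descriptive plan. It does not undermine the feasibility objectives.

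**What to change.** Add to the SAP and Protocol 11.4 one descriptive table, by arm at weeks 8 and 16:

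- the number and percent whose mean of Graded Chronic Pain items 2 to 4 rose from baseline by 1 or more and by 2 or more points. The documents set no cut-off, so these are assumptions shown as a range for the study team to confirm beforehand;
- the same for a rise in JFLS-8, with cut-offs and a rule for not-applicable items stated in advance;
- exact 95% CIs for each arm and the between-arm difference with its CI, with no test;
- the number assessed as denominator, and a bound counting missing participants as worsened;
- withdrawals for increased pain by arm, placed beside the adverse-event table.

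Reconcile Protocol 8.1.2, 8.1.3, 8.2 and Appendix J, II.A on which events are recorded, defined and reported. Also reconcile 6.4 with Appendix G and Appendix A on whether and when participants are asked about events.

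The cost is SAP wording and one table, with no new data, visits or staff. The downside is that some rises are natural fluctuation, so the counts must be read against the control arm and not as a count of harms.
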